### 7.2.2.3.1. *Events following premature discontinuation of the MDI sensor*

It is assumed that participants would continue to take MDI as they would have without the CIS intervention (jump to reference imputation) following discontinuation of the MDI sensor if receiving treatment Arms 3 and 4, otherwise continue to take MDI as they would have with their allocated CIS interventions (MAR).

It is assumed that participants would continue to take MDI as they would have with their allocated CIS interventions (MAR) following concurrent discontinuation of MDI sensor and withdrawal from study if unrelated to CIS.

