### **Randomization/treatment: Conditional Visits 2, 3 and 4 (V2, V3 and V4)**

Subjects who meet the randomisation inclusion criteria will be randomised to one of five CIS treatment arms at this visit (V2, V3 or V4). All treatment arms continue with Relvar/Breo ELLIPTA (ICS/LABA) maintenance therapy and Salbutamol MDI rescue therapy as in the run-in period and both inhalers continue having a sensor fitted. The treatment arms are defined by whether the data, from Relvar/Breo ELLIPTA (maintenance) or Relvar/Breo ELLIPTA (maintenance) and salbutamol MDI (rescue), is fed back to the subject or subject and HCP, or not at all. The 5 treatments arms are as follows:

1. Data on Maintenance use supplied to Subject (app) and HCP (dashboard)
2. Data on Maintenance use supplied to Subject (app)
3. Data on Maintenance and Rescue use supplied to Subject (app) and HCP (dashboard)
4. Data on Maintenance and Rescue use supplied to Subject (app)
5. No data supplied to Subject or HCP

Following randomisation, subjects in arms 1, 2, 3 and 4, will receive training on how to download and use the smart phone app, including how to connect and register the sensors via Bluetooth to their smart phone and to the app. Subjects in arm 5 who receive no data will be provided with a home hub so that their data will be uploaded during study, though they and their HCP will not see that data. Technical and operational details around registering sensors, connecting sensors to smart phone or a home hub and other details of app connectivity and function will be provided/referenced in the Study Reference Manual (SRM).

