## 2.3. Study Design

Overview of Study Design and Key Features	
	[GlaxoSmithKline Document Number 2016N307903_01 ].
Time & Events	Refer to Appendix 1 : Schedule of Activities
Treatment Assignment	
All randomised participants will receive Relvar/Breo ELLIPTA, at the dose allocated at the run in. Salbutamol Metered Dose Inhaler (MDI) rescue medication will be prescribed to participants to use as needed throughout the study for relief of asthma symptoms as per usual practice
 
All participants will have sensors attached to both their Relvar/Breo ELLIPTA and salbutamol MDI. It is the type of data provided by the CIS (either Relvar/Breo ELLIPTA alone or Relvar/Breo ELLIPTA and salbutamol MDI), as well as who sees that data, (participant alone or participant and HCP), that defines the treatment arms.
 
Participants will be randomized 1:1:1:1:1 to one of the five treatments arms for the duration of the treatment period:
 

• Arm 1: Data on Maintenance use supplied to Participant (app) and HCP (dashboard)

• Arm 2: Data on Maintenance use supplied to Participant (app)

• Arm 3: Data on Maintenance and Rescue use supplied to Participant (app) and HCP (dashboard)

• Arm 4: Data on Maintenance and Rescue use supplied to Participant (app)

• Arm 5: No data supplied to Participant or HCP

 
The treatment period for the study is 6 months. However, due to the flexible run in period a participant could be on the study for approximately 7, 8 or 9 months in total.
 
GSK RandAll NG will be used to generate the randomisation schedule. Centralized randomisation will be used. GSK RAMOS NG will be used for treatment allocation.

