**Table 4**

Intercurrent Event Estimation Rules (to be applied sequentially)	Intercurrent Event (IE)	Strategy with Rationale	Estimation Method following IE
1	
None (completed as randomised)
 
Without discontinuation of CIS feedback or MDI eSensor
 
 
Premature discontinuation from ELLIPTA eSensor
 
Premature discontinuation from ELLIPTA
 
Change of dose of ELLIPTA
 
 
Discontinuation of CIS feedback, but not MDI eSensor
 
 
Premature discontinuation from App and/or HCP interaction
 
	
Treatment policy:
 
Directly assessed using observed rescue data while MDI sensor is in use, regardless of whether the CIS feedback is discontinued.
	Data are available; no imputation required

Intercurrent Event Estimation Rules (to be applied sequentially)	Intercurrent Event (IE)	Strategy with Rationale	Estimation Method following IE
2	Discontinuation from MDI eSensor but not the study	Hypothetical:	MAR imputation (Arms 1&2) J2R imputation (Arms 3&4)
3	Premature withdrawal from the study	Hypothetical:	MAR imputation (Arms 1&2) J2R imputation (Arms 3&4)
4	Premature withdrawal from the study not related to CIS, and concurrent with discontinuation of the MDI sensor	Hypothetical:	Missing at Random (MAR) Imputation

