### Intercurrent Event Patterns

### Intercurrent Event 'Estimation Rules' 1-4

a. J2R imputation if withdrawal related to CIS; MAR imputation if withdrawal not related to CIS

Percentage of Rescue Free Days Endpoint
Intercurrent Events related to CIS
In order to implement the intercurrent event strategy detailed in Section 7.2.2.3 Strategy for Intercurrent (Post-Randomisation) Events, it is necessary to determine if and when the reasons for permanent discontinuations related to CIS occur.
The date and reason for withdrawing from the study will be determined from the study conclusion page of the eCRF.
Study discontinuation reasons classified as related to CIS are as follows:

 
Withdrew consent – dissatisfaction with the connected inhaler system (CIS)
 

Percentage of Rescue Free Days Endpoint
Monthly Percentage of Rescue Free Days - Calculation
STEP 1: Creating the observed adherence dataset (Observed Dataset A)
To determine the monthly observed percentage of rescue free days values (Observed Dataset A) the following should be applied for each month:
For Baseline Analysis Month, for each participant create a count of each of the following types of Days
D1 = Rescue use recorded
D2 = Device incident
D3 = Post discontinuation of MDI rescue sensor
D4 = MDI rescue free
D5=D1 + D2 + D3 + D4, i.e. The total number of days within the Baseline Analysis Month; the total number of days between Beginning Timepoint and Ending Timepoint as defined in Table 5 in Section 10.2 Appendix 2: Assessment Windows .
For Analysis Month 1, 2, 3, 4 and 5, for each participant create a count of each of the following types of days:
D1 = Rescue use recorded
D2 = Device incident
D3 = Post discontinuation of MDI rescue sensor
D4 = MDI rescue free
D5 = D1 + D2 + D3 + D4, i.e. The total number of days within the Analysis Month; the total number of days between Beginning Timepoint and Ending Timepoint as defined in Table 5 in Section 10.2 Appendix 2: Assessment Windows .
For Analysis Month 6, for each participant create a count of each of the following types of days:
D1 = Rescue use recorded
D2 = Device incident
D3 = Post discontinuation of MDI rescue sensor
D4 = MDI rescue free

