Implement special case of MAR post-early discontinuation of study by identifying participants where the MDI rescue sensor is prematurely discontinued and the participant concurrently withdraws from the study. Where study withdrawal has not been discontinued after the sensor but on the same day,  $r2=0$ .

- If the sensor is in use for at least a day within a month,  $r1>0$  then let the analysis value be a combined value (weighted average) of the J2RA observed and MARB imputed values, by taking a proportion of each value based on the proportion of days the MDI rescue was in use and not in use in that month

Analysis Value =  $r1/r4 \times (\text{value from J2RA}) + r3/r4 \times (\text{value from MARB})$

Note the weights are r4

- Else if the sensor was not used in the month,  $r1=0$  then let the analysis value be the imputed value,  
 Analysis value = value from MARA dataset (which is the imputed value)

For Arm 3 and 4,

- If the sensor is in use for at least a day within a month,  $r1>0$  then let the analysis value be a combined value (weighted average) of the J2RA observed and J2RB imputed values, by taking a proportion of each value based on the proportion of days the MDI sensor is in use and not in use in that month

Analysis value =  $r1/r4 \times (\text{value from J2RA}) + (r2+r3)/r4 \times (\text{value from J2RB})$

Note the weight is, r4

- Else if the sensor was not used in the month,  $r1=0$  then let the analysis value be the imputed value,  
 Analysis value = value from J2RA dataset (which is the imputed value)

Implement special case of MAR post-early discontinuation of study by identifying participants where the MDI rescue sensor is prematurely discontinued and the participant concurrently withdraws from the study and study withdrawal reason is not related to CIS. Where study withdrawal has not been discontinued after the sensor but on the same day,  $r2=0$ .

- If the sensor is in use for at least a day within a month,  $r1>0$  then let the analysis value be a combined value (weighted average) of the J2RA observed and MARB imputed values, by taking a proportion of each value based on the proportion of days the MDI rescue was in use and not in use in that month

Analysis Value =  $r1/r4 \times (\text{value from J2RA}) + r3/r4 \times (\text{value from MARB})$

Note the weights are r4

- Else if the sensor was not used in the month,  $r1=0$  then let the analysis value be the imputed value,  

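### Rescue free days: the imputation rules after an MDI sensor stop or study withdrawal contradict one another and in part ignore which feedback the participant still receives

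*SAP*

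**What the plan says.** **Arms.** Arm 3 is "Arm 3: Data on Maintenance and Rescue use supplied to Participant (app) and HCP (dashboard"; Arm 1 is "Data on Maintenance use supplied to Subject (app) and HCP (dashboard" (Protocol 5.1). Arms 4 and 2 are the same pair without the HCP. Arm 5, the reference, gets no feedback.

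**SAP 7.2.2.3, Table 4.** Rule 2 (MDI sensor stopped, participant stays in the study) and rule 3 (study withdrawal) both read "MAR imputation (Arms 1&2) J2R imputation (Arms 3&4". Rule 4 assigns MAR to "Premature withdrawal from the study not related to CIS, and concurrent with discontinuation of the MDI sensor".

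**SAP 7.2.2.3.1.** After an MDI sensor stop, participants are assumed to use rescue medication "as they would have without the CIS intervention (jump to reference imputation) following discontinuation of the MDI sensor if receiving treatment Arms 3 and 4". Those in the remaining arms are assumed to "otherwise continue to take MDI as they would have with their allocated CIS interventions (MAR". Its second paragraph ties MAR after concurrent sensor stop and withdrawal to withdrawal that is unrelated to the CIS.

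**SAP 10.5.3.2, Step 4.**
- Arms 1 and 2, general rule: a MAR value (MARB) fills the unobserved part of a partly observed month. A month with no sensor use (r1 = 0) takes the J2RA value.
- Arms 1 and 2, special case where "the MDI rescue sensor is prematurely discontinued and the participant concurrently withdraws from the study": MAR values throughout, with no condition on the reason.
- Arms 3 and 4: J2R in general. Concurrent leavers are split by reason: MAR if not CIS-related, J2R if CIS-related.

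Footnote a to the rescue schematic says "J2R imputation if withdrawal related to CIS; MAR imputation if withdrawal not related to CIS".

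**Adherence endpoint.** Table 3 rule 1 (SAP 7.1.4) lists stopping the MDI sensor among events that leave CIS feedback and the ELLIPTA sensor in place. Footnote b in SAP 10.5.3.1 gives J2R for a CIS-related withdrawal.

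**The concern.** J2R suits someone who has lost the intervention; MAR suits someone who can be assumed to go on as allocated. The choice should follow from what feedback remains and why the participant left. Table 4 rules 2 and 3 choose by arm instead, and Step 4 does not fully carry out Table 4.

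Two programmers following different sections would therefore produce different data for the same participant. The estimates for Arms 1 to 4 against Arm 5 would also rest on differing assumptions about the same kind of event.

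**Working it through.** The documents give no sample size, effect or dropout figure for rescue free days, so there is no stated number to reproduce. The check traces each event through the rules, then applies Step 4 to the SAP's own example records. Those values are dummies: they show that the rules differ, not the direction or size of any real effect. Months 4 to 6 are averaged with equal weight, each having 28 days.

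**(a) Arms 1 and 2, CIS-related withdrawal with concurrent sensor stop.**
- Table 4 rule 3: MAR, whatever the reason. The CIS condition in rule 4 therefore changes nothing in these arms.
- Step 4 special case: MAR, no condition on the reason.
- Same event in Arms 3 and 4: J2R. Same event for adherence: J2R.

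Second example in Step 4 (sensor stop and withdrawal after day 20 of month 5). Inputs: month 4 = 75; month 5 observed 83, MARB 79, J2RB 77; month 6 MARA 75, J2RA 77.
- MAR: month 5 = (20 × 83 + 8 × 79)/28 = 81.86; endpoint = (75 + 81.86 + 75)/3 = 77.29.
- J2R: month 5 = (20 × 83 + 8 × 77)/28 = 81.29; endpoint = (75 + 81.29 + 77)/3 = 77.76.

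**(b) Arms 1 and 2, wholly unobserved month.** First example (sensor stopped after day 20 of month 5, withdrawal after day 5 of month 6). Inputs: month 4 = 77; month 5 observed 71, MARB 78; month 6 has r1 = 0, J2RA 80, MARA 77.
- Month 5 under either reading: (20 × 71 + 8 × 78)/28 = 73.00.
- Step 4 as written (month 6 from J2RA): (77 + 73.00 + 80)/3 = 76.67.
- Table 4 and 7.2.2.3.1 (month 6 under MAR): (77 + 73.00 + 77)/3 = 75.67.

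One record, two values, 1.00 point apart. As written, Step 4 also gives this participant MAR for the tail of month 5 and J2R for all of month 6.

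**(c) Arms 3 and 4, MDI sensor stop only.** Rule 2 does not ask whether the ELLIPTA sensor, app or dashboard continue. If they do, an Arm 3 participant has the data flow of Arm 1, and an Arm 4 participant that of Arm 2. The SAP nevertheless imputes from Arm 5, on a premise of no CIS that Table 3 rule 1 contradicts.

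Shift in the arm mean = f × D, where f is the share of months 4 to 6 time imputed after such stops and D is the effect of maintenance feedback on rescue free days. Neither is in the documents. Assuming f = 2–15% and D = 5–15 points:
- 0.02 × 5 = 0.1 point
- 0.10 × 10 = 1.0 point
- 0.15 × 15 = 2.25 points

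If D is positive, the shift is toward no difference from Arm 5.

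**The case against.** - **Arms 1 and 2 never had rescue feedback, so losing the MDI sensor changes nothing for them.** This stands for a sensor-only stop, where MAR is reasonable. It does not cover a CIS-related withdrawal, where maintenance feedback goes too.
- **For a rescue endpoint the MDI sensor is what carries the rescue feedback, so J2R in Arms 3 and 4 is the conservative choice.** This stands in part. The match between Arm 3 without rescue data and Arm 1 requires the ELLIPTA sensor, app and dashboard all to continue, and it ignores earlier exposure to rescue feedback. Using Arm 1 or 2 as reference is therefore a judgement, not a correction of an outright error.
- **Table 4 labels rules 2 to 4 hypothetical, so MAR may be a deliberate estimand.** The same label covers MAR in Arms 1 and 2 and J2R in Arms 3 and 4 for the same event, so it cannot explain the split. Any rationale that followed the label may have been lost in the text conversion, and its absence is not held against the plan.
- **SAP 7.2.2.3.1 already gives Arms 1 and 2 MAR in its first sentence without a reason test.** True. The section is ambiguous for these arms; only its second paragraph attaches the CIS condition.
- **Footnote a is weak evidence.** Also true. The schematic is not visible, so the footnote may apply only to Arms 3 and 4, where it agrees with Step 4. It is a place to align, not proof of a contradiction.
- **Few participants may be affected.** Amendment 01 reports dropout much lower than expected, which favours the low end of any range.

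**Conclusion.** The rules need correcting. Limb (a) is a mismatch between the imputation and the reason for leaving, and limb (b) is a direct contradiction between Table 4 and Step 4. Limb (c) rests on a premise that the SAP's own Table 3 does not share, though its best remedy is open to debate.

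Two stronger readings do not hold. A reader might infer that Arms 1 and 2 are systematically protected from J2R. They are not: under Step 4 as written, anyone in those arms whose sensor stopped before withdrawal, or who stayed in the study, gets J2RA for whole missing months. Limb (a) therefore applies mainly to concurrent leavers and to partly observed months. A reader might also infer that a planned estimate of the value of rescue feedback is distorted. For rescue free days SAP 7.2.2.5 plans only Arms 1 to 4 against Arm 5; the Arm 1 v 3 and Arm 2 v 4 contrasts in SAP 7.3 concern adherence.

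The effect is confined to four descriptive comparisons on a secondary endpoint, with no formal inference planned (SAP 2.4). Its real size cannot be computed. The 1.00-point difference comes from one dummy record, and the 0.1 to 2.25 points for limb (c) depend wholly on the assumed f and D.

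**What to change.** Before unblinding, amend the SAP as follows.

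1. CIS-related withdrawal: J2R to Arm 5 in all of Arms 1 to 4. Add the reason condition to Table 4 rule 3 and to the Step 4 special case for Arms 1 and 2.
2. Step 4, Arms 1 and 2, r1 = 0: replace J2RA with MARA when withdrawal is not CIS-related.
3. Arms 3 and 4, MDI sensor stopped but ELLIPTA sensor and app (and, in Arm 3, dashboard) retained: add an imputation with Arm 1 as reference for Arm 3 and Arm 2 for Arm 4, at least as a sensitivity analysis. Keep J2R to Arm 5 when all feedback has stopped.
4. State the rule for unrelated withdrawal after an earlier sensor stop, which is the pattern in the SAP's first worked example.
5. Align Table 4, 7.2.2.3.1, the schematic footnote and every branch of Step 4, naming the arms each covers.

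The cost is SAP wording plus extra imputation sets and seeds beyond the four Part 2B sets now listed for this endpoint. No new data are needed for the withdrawal rule: the study conclusion page of the eCRF already records dissatisfaction with the CIS as a reason.

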### 7.2.2.4. **Statistical Analyses / Methods**

Details of the planned displays will be provided in Section 10.8, [Appendix 8: List of Data Displays](#) and will be based on GSK data standards and statistical principles.

Unless otherwise specified, endpoints /variables defined in Section 7.2.2 MDI Rescue Medication Use Endpoints, Section 7.1.1 Endpoint will be summarised using descriptive statistics, graphically presented (where appropriate) and listed.

### 7.2.2.5. **Statistical Analyses / Methodology Specification**

Endpoint / Variables
The percentage of rescue free days measured between the beginning of month 4 and the end of month 6 as determined by the MDI rescue sensor for the following treatment arm comparisons
Multiple Imputation Specification

Imputation will be carried out using monthly rescue free rates for months 1 to 6. 1000 draws will be used. For each draw, four intermediate imputation datasets will be created to allow for the handling of fully unobserved months (using set A imputations) and partially unobserved months (using set B imputations).
 
 
Set A where the partially observed month is directly estimated under the MAR assumption as the proportion of the number of days a participant is adherent divided by the number of days data provided in that month. 
 
J2R imputations
 
MAR imputations
 
 
 
Set B where the partially observed month is set to missing. 
 
J2R imputations
 
MAR imputations
 
 
 
 
The timing of the intercurrent events of discontinuation of the MDI sensor and withdrawal from study will be used to identify the proportion of each month to be assigned as observed data, J2R imputed data or MAR imputed data. The strategy for handling intercurrent events is described in Section 7.2.2.3 Strategy for Intercurrent (Post-Randomisation) Events.

Within each imputation draw, for each month, the observed and any imputed data will be combined to provide a percentage rescue free day value. The values for months 4 to 6 will be combined to create the value for the secondary analysis and the weight to be assigned to each participant.

Multiple imputation using Rubin's rules will be used to estimate the treatment effect and associated standard error, by performing the ANCOVA analysis described below on the secondary endpoint within each dataset.

The multiple imputation will be implemented using the methods described in Carpenter, 2013, using the macros available from <https://missingdata.lshtm.ac.uk/2017/04/06/qsk-five-macros/>.

### Model Specification

The analysis will be performed on the percentage of rescue free days between Months 4 and 6 using an Analysis of Covariance (ANCOVA) model allowing for effects due to randomised treatment arm, baseline rescue free days percentage, duration of run-in (visits), country, gender, and age (years).

Baseline rescue free days will be the percentage rescue free days during the last 28 days of the run-in period prior to randomisation. Randomised treatment, duration of run-in (visits), country, and gender will be included as categorical covariates; baseline rescue free days percentage and age (years) will be included as continuous covariates.

Each participant will be weighted by the proportion of months 4 to 6 for which data is included in the percentage rescue free days endpoint (both observed and imputed data are accounted for in the weighting).

Data from all 5 treatment arms will be included in the model, and used to estimate the difference between:

- Arm 1 and Arm 5
- Arm 2 and Arm 5
- Arm 3 and Arm 5
- Arm 4 and Arm 5

### Model Checking & Diagnostics

Normality assumptions underlying the ANCOVA model used for analysis will be examined in a limited number of imputed datasets by obtaining a normal probability plot of the residuals and a plot of the residuals versus the fitted values (i.e. checking the normality assumption and constant variance assumption of the model respectively) to gain confidence that the model assumptions are reasonable.

If there are any departures from the distributional assumptions, alternative models may be explored using appropriately transformed data.

Interactions with treatment will be explored for other model covariates and tests for interactions will be at the 2-sided 10% significance level. Any significant interactions that are found will be thoroughly investigated and where necessary, extra outputs will be produced.

### Model Results Presentation

Summary statistics (mean, standard deviation, median, minimum, maximum) of the primary endpoint will be provided, based on the observed percentages.

The adjusted means for each treatment and the estimated treatment difference for the treatment comparisons of Arm 1 versus Arm 5, Arm 2 versus Arm 5, Arm 3 versus Arm 5 and Arm 4 versus Arm 5 will be presented together with the 95% confidence interval for the differences and corresponding p-values from

the multiple imputation procedure.

Endpoint / Variables
Total rescue use measured between the beginning of month 4 and the end of month 6 as determined by the MDI rescue sensor
Summary

The endpoint will be summarised using descriptive statistics (n, mean, SD, median, min, max) for each treatment arm.
 
To explore the effect of 6 months use of the CIS on a participant's rescue medicine usage, the following displays will be presented,
 
 
Summary statistics (n, mean, SD, median, min, max) of Total rescue use measured between the beginning of month 4 and the end of month 6 as determined by the MDI rescue sensor
 
Total rescue use will be summarized by each individual month (Month 1 – Month 6) and then displayed as a total between month 4 – 6.
 

